2. GENERAL ANALYSIS DEFINITIONS

2.1. Visit Windows

Unless otherwise specified, actual scheduled visits will be used for over time summaries and listings with no visit windows applied.

2.2. Analysis Sets

2.2.1. Randomized Analysis Set

The randomized analysis set includes all participants who are randomized in the study. Participants in the Randomized Analysis Set will be analyzed according to the randomized study intervention regardless of the study intervention they actually received.

2.2.2. Efficacy Analysis Set(s)

Unless otherwise specified, all efficacy analyses will be based on the Full Analysis Set (FAS), which includes all randomized participants who receive at least 1 (partial or complete) dose of study intervention. Participants in FAS will be analyzed according to the randomized study intervention regardless of the study intervention they actually received.

2.2.3. Safety Analysis Set

The safety analysis set includes all randomized participants who receive at least 1 (partial or complete) dose of study intervention. Participants in the Safety Analysis Set will be analyzed according to the study intervention they actually received.

2.2.4. Pharmacokinetics Analysis Set

The PK analysis set includes all randomized participants who receive at least 1 (complete) dose of study intervention (golimumab or guselkumab) and have at least 1 valid blood sample drawn for PK analysis after their first dose of study intervention (golimumab or guselkumab). Participants in the Pharmacokinetics Analysis Set will be analyzed according to the study intervention they actually received.

2.2.5. Immunogenicity Analysis Set

The immunogenicity analysis set is defined as all participants who receive at least 1 (partial or complete) dose of guselkumab and/or golimumab and have appropriate samples for detection of antibodies to guselkumab and/or to golimumab (ie, participants with at least 1 sample obtained after their first dose of guselkumab or golimumab, respectively). Participants in the Immunogenicity Analysis Set will be analyzed according to the study intervention they actually received.

2.3. Definition of Subgroups

The primary endpoint will be evaluated for subgroups based on demographics and baseline UC clinical disease characteristics, UC-related concomitant medication usage, and UC-related medication history.

Demographics

- Gender (male, female)
- Race (Caucasian, non-Caucasian)
- Baseline age (\leq median age, $>$ median age)
- Baseline body weight (\leq 1st quartile, $>$ 1st quartile and \leq 2nd quartile, $>$ 2nd quartile and \leq 3rd quartile, $>$ 3rd quartile)
- Baseline body mass index (BMI) (\leq 1st quartile, $>$ 1st quartile and \leq 2nd quartile, $>$ 2nd quartile and \leq 3rd quartile, $>$ 3rd quartile)
- Tobacco use status (non-user, prior user, current user)
- Region
 - Eastern Europe: Poland, Russia, Ukraine
 - Latin America: Argentina, Mexico, Brazil
 - Rest of World: United States, Germany, Australia

Baseline UC clinical disease characteristics

- UC disease duration (\leq 5 years, $>$ 5 years to \leq 15 years, $>$ 15 years)
- Extent of disease (limited, extensive)
- Severity of UC disease (moderately active: $6 \leq$ Mayo score \leq 10, severely active: Mayo score $>$ 10)
- Severity of endoscopic disease (moderate: endoscopic subscore = 2, severe: endoscopic subscore = 3)
- CRP (\leq 3 mg/L, $>$ 3 mg/L)
- CRP (\leq 1st quartile, $>$ 1st quartile and \leq 2nd quartile, $>$ 2nd quartile and \leq 3rd quartile, $>$ 3rd quartile)
- Fecal calprotectin (\leq 250 mg/kg, $>$ 250 mg/kg)

- Fecal calprotectin (\leq 1st quartile, $>$ 1st quartile and \leq 2nd quartile, $>$ 2nd quartile and \leq 3rd quartile, $>$ 3rd quartile)

Baseline UC-related concomitant medications

- Oral 5-aminosalicylic acid [5-ASA] compounds (receiving, not receiving)
- Oral corticosteroids including budesonide and beclomethasone dipropionate (receiving, not receiving)
- Participants taking conventional immunomodulators (6-MP/AZA/MTX) during Screening but discontinuing it prior to Week 0
- Participants taking Vedolizumab during Screening but discontinuing it prior to Week 0

UC-related medication history

- Refractory or intolerant to 6-MP/AZA (yes, no)
- Refractory, dependent or intolerant to oral or IV corticosteroids (yes, no)
- Refractory, dependent, or intolerant to oral or IV corticosteroids, but not refractory or intolerant to 6-MP/AZA (yes, no)
- Refractory, dependent or intolerant to oral or IV corticosteroids, and refractory or intolerant to 6-MP/AZA (yes, no)
- Refractory or intolerant to Vedolizumab (yes, no)
- Vedolizumab experienced (yes, no)
- Refractory or intolerant to Tofacitinib (yes, no)
- Tofacitinib experienced (yes, no)

2.4. Study Day and Relative Day

Study Day 1 refers to the date of the first study intervention administration. All efficacy and safety assessments at all visits will be assigned a day relative to this date.

Study day for a visit is defined as:

- Visit date - (date of Study Day 1) +1, if visit date is \geq date of Study Day 1
- Visit date - date of Study Day 1, if visit date $<$ date of Study Day 1

There is no 'Study Day 0'.

2.5. Baseline

Baseline is defined as the last observation prior to or on the day of the first study intervention, unless otherwise specified.

2.6. Imputation Rules for Missing AE Date/Time of Onset/Resolution

Partial adverse event (AE) onset dates will be imputed as follows:

- If the onset date of an adverse event is missing day only, it will be set to:
 - First day of the month that the AE occurred, if month/year of the onset of AE is different than the month/year of the date of the first study intervention administration
 - The day of the first study intervention administration, if the month/year of the onset of AE is the same as month/year of the first study intervention administration and month/year of the AE resolution date is later
 - The day of the first study intervention administration or day of AE resolution date, whichever is earliest, if month/year of the onset of AE and month/year of the first study intervention administration date and month/year of the AE resolution date are same
- If the onset date of an adverse event is missing both day and month, it will be set to the earliest of:
 - January 1 of the year of onset, as long as the year is the same or after the year of the first study intervention administration
 - Month and day of the first study intervention administration, if this date is the same year that the AE occurred
 - Last day of the year if the year of the AE onset is prior to the year of the first study intervention administration
- Completely missing onset dates will not be imputed.

Partial AE resolution dates not marked as ongoing will be imputed as follows:

- If the resolution date of an adverse event is missing day only, it will be set to the earliest of the last day of the month of occurrence of resolution or the day of the date of death, if the death occurred in that month.
- If the resolution date of an adverse event is missing both day and month, it will be set to the earliest of December 31 of the year or the day and month of the date of death, if the death occurred in that year.
- Completely missing resolution dates will not be imputed.

AE onset/resolution dates with missing times will be imputed as follows:

- A missing time of onset of an adverse event will be set to:
 - 00:01 as long as the onset date is after the study intervention start date
 - The time of the study intervention start date if this is the same day the AE occurred.
- The missing time of resolution of an adverse event will be set to 23:59.

If a missing time is associated with a partial or missing date, the date will be imputed first prior to imputing the time.

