5.3. Lifestyle Considerations

Potential participants must be willing and able to adhere to the following lifestyle restrictions during the course of the study to be eligible for participation:

1. Refer to Section 6.5, Concomitant Therapy for details regarding prohibited and restricted therapy during the study.
2. Agree to follow all requirements that must be met during the study as noted in the Inclusion and Exclusion Criteria (eg, contraceptive requirements).
3. Must agree not to receive a live virus or live bacterial vaccination, including a BCG vaccination, during the study and for 12 months after receiving study intervention for BCG vaccination or 12 weeks after receiving the last administration of study

intervention for other live vaccines.

4. Must not receive guselkumab or golimumab outside of this protocol or participate in any other clinical study with an investigational agent while in this study, and must terminate study participation if they do. A participant who intends to participate in any other clinical study with an investigational agent should complete the Week 12 visit or early termination visit as described in Section 1.3 before he or she terminates study participation.
5. Must be willing and able to complete daily diaries to document clinical symptoms, AEs, etc.

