The sponsor will register and disclose the existence of and the results of clinical studies as required by law.

DATA QUALITY ASSURANCE

Data Quality Assurance/Quality Control

Steps to be taken to ensure the accuracy and reliability of data include the selection of qualified investigators and appropriate study sites, review of protocol procedures with the investigator and study-site personnel before the study, periodic monitoring visits by the sponsor, and direct transmission of clinical laboratory data from a central laboratory into the sponsor's data base. Written instructions will be provided for collection, handling, storage, and shipment of samples.

Guidelines for eCRF completion will be provided and reviewed with study-site personnel before the start of the study.

The sponsor will review eCRF for accuracy and completeness during on-site monitoring visits and after transmission to the sponsor; any discrepancies will be resolved with the investigator or designee, as appropriate. After upload of the data into the study database they will be verified for accuracy and consistency with the data sources.

CASE REPORT FORM COMPLETION

Data for each study participant will be collected in the eCRF or ancillary data collection systems such as the IWRS, PRO tablets, laboratory database, and imaging database. Case report forms are prepared and provided by the sponsor for each participant in electronic format. Collectively, all data collection via eCRFs and ancillary systems will comprise what is referred to in this protocol as the DCS.

All DCS entries, corrections, and alterations must be made by the investigator or authorized study-site personnel.

The investigator must verify that all data entries in the eCRF are accurate and correct.

Study data will be transcribed by study-site personnel from source documentation to an eCRF or the appropriate ancillary DCS, as applicable. Study-specific data from each source will be transmitted in a secure manner to the sponsor.

Worksheets may be used as source documentation to capture data and facilitate completion of the eCRF or entry of data into the applicable ancillary data system. Data must be entered into the DCS in English. The eCRF must be completed as soon as possible after a participant visit and the forms should be available for review at the next scheduled monitoring visit.

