6.1. Adverse Events

The verbatim terms used in the eCRF by investigators to identify AEs will be coded using the Medical Dictionary for Regulatory Activities (MedDRA). Treatment-emergent AEs (TEAEs) are AEs with onset during the intervention phase or that are a consequence of a pre-existing condition that has worsened since baseline. All reported AEs which are treatment-emergent will be included in the analysis. For each AE, the count and percentage of participants who experience at least 1 occurrence of the given event will be summarized by intervention group.

The following analyses of TEAEs will be used to assess the safety of participants:

- Frequency and type of AEs
- Frequency and type of SAEs
- Frequency and type of reasonably related AEs as assessed by the investigator
- Frequency and type of AEs leading to discontinuation of study intervention
- Frequency and type of infections (including COVID-19 infections)
- Frequency and type of serious infections
- Frequency and type of infections requiring oral or parenteral antimicrobial treatment
- Frequency and type of AEs temporally associated with infusion
- Frequency and type of injection-site reactions

Since safety should be assessed relative to exposure and follow-up, all AE summary tables will summarize the average weeks of follow-up and average exposure (number of administrations) for each treatment group.

In addition to the summary tables, a by-subject listing will be provided for deaths that occurred during the study and, respectively, for the following TEAEs:

1. SAEs
2. AEs that led to permanent discontinuation of study intervention
3. Serious infections including TB
4. COVID-19 infections
5. Anaphylactic reactions or serum sickness reactions
6. Malignancies

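### Minor, wrong as written: SAP 2.6 dates a year-only adverse event in the first-dose year to January 1, before dosing, and the printed hemoglobin-increase row in Attachment 7 grades every realistic value as an increase

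*SAP*

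**What the plan says.** **Onset dates (SAP 2.6).** For a year-only onset the SAP states: "If the onset date of an adverse event is missing both day and month, it will be set to the earliest of" three candidates. They are January 1 of the onset year, if that year is the first-dose year or later; "Month and day of the first study intervention administration, if this date is the same year that the AE occurred"; and the last day of the onset year, if that year is before the first-dose year.

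Where only the day is missing and the onset month is the first-dose month, the same section depends on resolution. With resolution in a later month, onset becomes the first-dose day ("The day of the first study intervention administration, if the month/year of the onset of AE is the same" and resolution is later). With resolution in the same month, onset is the earlier of the first-dose day and the resolution day. Partial resolution dates are imputed late: "If the resolution date of an adverse event is missing both day and month, it will be set to the earliest of December 31" or the date of death in that year. A completely missing resolution date is not imputed.

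SAP 6.1 defines TEAEs as "AEs with onset during the intervention phase or that are a consequence of a pre-existing condition that has worsened since baseline". The adverse event analyses use TEAEs, and "a by-subject listing will be provided for deaths that occurred during the study and, respectively, for the following TEAEs": serious events, events leading to permanent discontinuation, serious infections, COVID-19 infections, anaphylactic or serum sickness reactions, and malignancies.

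**Hemoglobin grades (SAP Attachment 7, used in SAP 6.2).** The hemoglobin-increase row is printed as Grade 1 from above 0 to 2 x ULN, Grade 2 from above 2 to 4 x ULN, and Grade 3 above 4 x ULN. SAP 6.2 plans a maximum-grade summary and a shift table that names hemoglobin, and says grading follows CTCAE version 5.0.

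**The concern.** The first-dose candidate has a purpose only if it can sometimes set the date. Under a rule that takes the minimum, it cannot. The result also runs against the day-only rule, which keeps an event on the first-dose day unless it resolved earlier in that month.

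TEAE status turns on the onset date, so a year-only event that may well have begun after dosing would be classed as pre-treatment. It would be absent from both the TEAE table and the matching TEAE listing, so the listing would not reveal the omission. The error has one direction, toward under-counting, and safety of the combination is a primary objective of the first 12 weeks.

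The hemoglobin row is unrelated in mechanism but equally plain. A grade for an increase that includes normal and low values cannot identify an increase.

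**Working it through.** There is no plan figure to reproduce. The check applies the printed rules literally.

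**1. Year-only onset, current rule.** Let F be the first-dose date and Y the onset year.

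- Y before the year of F: December 31 of Y.
- Y after the year of F: January 1 of Y.
- Y equal to the year of F: min(January 1 of Y, F) = January 1 of Y.

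Over every possible F in a 365-day year, the imputed onset falls before dosing for 364 dates (365 of 366 in a leap year). The exception is F = January 1. The first-dose candidate decides the date in 0 cases. For 308 of 365 dates (309 of 366), January 1 also precedes the whole 8-week screening window (Protocol 1.3). Adverse event collection starts only at consent (Protocol 8.3.1).

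Example: F = 15 June 2019, with study day as in SAP 2.4.

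| Recorded onset | Imputed date | Study day |
|---|---|---|
| 2018 | 31 December 2018 | -166 |
| 2019 | 1 January 2019 | -165 |
| 2020 | 1 January 2020 | 201 |

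Only the middle row is a problem.

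**2. Corrected rule for Y equal to the year of F.** Onset = min(F, R), where R is the resolution date after the SAP's own imputation; if R is absent, onset = F. With F = 16 September 2019 and onset recorded as 2019:

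| Recorded resolution | R | Onset | Status |
|---|---|---|---|
| none | none | 16 September | TEAE |
| 20 October 2019 | 20 October | 16 September | TEAE |
| 1 September 2019 | 1 September | 1 September | pre-treatment |
| August 2019 | 31 August | 31 August | pre-treatment |
| September 2019 | 30 September | 16 September | TEAE |
| 2019 | 31 December | 16 September | TEAE |

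The current rule gives 1 January 2019 in all six rows. I checked every first-dose date against every type of resolution record: 365 x (365 complete + 12 month-only + 1 year-only + 1 absent) = 365 x 379 = 138,335 combinations. The event is pre-treatment exactly when its resolution is known to precede first dose, with 0 mismatches. This tests the wording of the fix; it says nothing about how often the case occurs.

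**3. Scale.** The number of year-only onsets is not in the documents. Assuming 0, 1 or 2 affected participants in an arm of 70, incidence is understated by 0, 1/70 = 1.4 or 2/70 = 2.9 percentage points.

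**4. Hemoglobin.** ULN and LLN are not given; I assume ULN 15 to 18 g/dL and LLN 12 g/dL. Printed Grade 1 increase then runs from above 0 to 30-36 g/dL.

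| Value (g/dL) | Increase grade | Decrease grade |
|---|---|---|
| 7.9 | 1 | 3 |
| 9 | 1 | 2 |
| 11 | 1 | 1 |
| 14 | 1 | 0 |
| 17 | 1 | 0 |

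All 8 chemistry increase rows (ALT, AST, alkaline phosphatase, bilirubin, corrected calcium, creatinine, potassium, sodium) start Grade 1 above ULN. The other two hematology increase rows (lymphocytes, total WBC) have no Grade 1.

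**The case against.** The strongest reply is that nothing of consequence follows. Year-only onsets should be rare. Visits are every two weeks through Week 12, participants "Must be willing and able to complete daily diaries to document clinical symptoms, AEs, etc", and "The sponsor will review eCRF for accuracy and completeness during on-site monitoring visits and after transmission to the sponsor", with discrepancies resolved with the investigator. Serious events, malignancies and active TB are reported within 24 hours (Protocol 8.3.1, 8.3.5), so the gravest classes are the least likely to lack a month. The rule is the same in every arm, and no formal safety comparison is planned (SAP 6). All of this stands, and it keeps the point minor.

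A reader might infer that misdated events would vanish from the trial's safety record. The documents do not support that. Early discontinuations are summarized and listed with reasons (SAP 4.2), the monitoring committee receives monthly reports of all serious events (Protocol 9.5.1), and the deaths listing does not depend on TEAE status. What is lost is the event's place in the TEAE tables and TEAE listings.

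A reader might also take the day-only rule to use the first-dose day in every case. It does so only when resolution falls in a later month, so the contrast between the two rules is real but narrower than that.

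On hemoglobin, it is fair to say that SAP 6.2 does not state that the increase direction will be displayed. Inferring that the hemoglobin safety summaries as a whole are unreliable goes too far: decrease grades come from a separate row that is unaffected, and false Grade 1 values cannot enter a listing that starts at Grade 2. The text was read from PDF, so the original page should be checked, although the three cells are complete and consistent with one another.

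**Conclusion.** Both points hold as errors in the text, and both are minor.

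The onset rule gives a pre-dose date for every year-only event in the first-dose year unless dosing began on January 1. Such an event leaves the TEAE outputs unless it counts as a worsened pre-existing condition. Onsets recorded in earlier or later years are not affected. The practical effect is probably nil or very small. The 1.4 and 2.9 point figures are arithmetic on assumed counts, not estimates.

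The hemoglobin-increase row, as printed, grades every realistic value as an increase. If that direction is tabulated, every participant is Grade 1 before and after dosing and the display carries no information. A true rise could hardly reach Grade 2, which would need more than 30-36 g/dL at the assumed ULN.

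**What to change.** **SAP 2.6.** For an onset with day and month missing whose year equals the first-dose year, set onset to the first-dose date, or to the adverse event resolution date (imputed if partial) if that is earlier. Leave the December 31 rule for prior years and the January 1 rule for later years as they are. The limit to the first-dose year matters. With onset recorded as 2019, resolution on 15 January 2020 and first dose on 10 February 2020, moving onset to the resolution date would place it outside its recorded year.

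The SAP should state the small downside: a screening event with no resolution date, or with one that could fall after dosing, will count as treatment-emergent. That is the conservative direction for safety.

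**Attachment 7.** Check the original page and reconcile the hemoglobin-increase row with CTCAE version 5.0, so that an increase grade requires a value above ULN. The documents do not give the intended cut-points, so none is proposed here.

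**Cost.** One rule line, one sentence on the downside and one table row, with no new data, tables or listings. The SAP treats the Week 12 database lock as still to come (SAP 1.2, 1.5). Making the change before then avoids altering TEAE classification after unblinding.

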3. INTERIM ANALYSIS AND DATA MONITORING COMMITTEE REVIEW

For the purpose of future clinical development planning, an IA was performed in April 2020 after the first 126 randomized participants (i.e., 60% of the planned sample size) completed their Week 12 visit or terminated their study participation before Week 12.

An external DMC has been established and are meeting periodically to review interim unblinded safety data to ensure the continuing safety of the participants enrolled in the study. The DMC consists of 2 physicians and a statistician. The DMC responsibilities, authorities, and procedures are documented in a separate DMC charter.

4. SUBJECT INFORMATION

The number of participants in each analysis set will be summarized by treatment group and overall for this study. In addition, the distribution of participants by region, country and site ID will be presented.

Descriptive statistics (mean, standard deviation (SD), median, interquartile (IQ) range, minimum and maximum) will be provided for continuous variables. Frequency distributions will be provided for categorical variables. No formal statistical analyses for treatment comparisons will be performed.

